Clinical assessments of disease activity will take place during the following visits:

- Visit 1 Screening
- Visit 2 Infusion 1 (**Baseline**)
- Visit 3 Infusion 2
- Visit 4 Infusion 3
- Visit 5 Infusion 4
- Visit 6 Infusion 5
- Visit 7 Infusion 6
- Visit 8 Safety Follow Up
- Visit 9 End of Study

Blood samples for safety assessments will be collected in as follows:

- Visit 1 Screening: after informed consent has been obtained, blood samples should be collected from a vein of the study's participant arm, these lab results will help assess the subject's eligibility.
- Visit 2 Infusion 1, (**Baseline**): safety laboratory samples should be collected from a vein of the study participant in order to set a start point of comparing with the laboratory results to obtain in the following visits. Although, laboratory samples are a requirement of this visit, in certain situations this requirement will be avoided, and the laboratory results obtained during Visit 1 Screening will be used as a Baseline. See some of these situations below:
 - Period of time between Visit 1 Screening and Visit 2 Infusion 1 (Baseline) is less than 10 days.
 - The study participant had no change in medical history or concomitant medications since Visit 1 Screening.
 - No changes in physical examination are identified by principal investigator during Visit 2 – Infusion 1, (Baseline).
- Visit 6 Infusion 5: safety laboratory samples should be collected from a vein of the study's participant arm during this visit.
- Visit 9 End of Study: safety laboratory samples should be collected from a vein of the study's participant arm during this visit.

For study participants who do not complete the study trial, a safety follow-up visit will be scheduled as follows:

- For subjects who did not receive any the investigational product, a safety follow-up visit, or Early termination visit (ETV) will be scheduled as soon as possible, but not later than 30 days after the last visit.
- For subjects who received at least one dose of the investigational product, a safety follow-up visit will be scheduled approximately 30 days after that single dose.
- For subjects who received more than one dose of the investigational product, a safety follow-up visit will be scheduled after the last investigational product administration.

Withdrawal Criteria

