- 10. Inject the contents into a 250cc bag of normal saline for injection

11. Properly label the infusion bag with the subject ID, D.O.B, preparation date, time and expiration and cover it with an amber bag.

Investigational Product Assignment (Randomization and Blinding)

A total of 24 eligible subjects will be randomized to either placebo (12) or active drug (12) (HB-adMSCs) in a 1:1 balanced design. The randomization will be applicable only to eligible subjects, if a subject is not eligible during the screening process for study participation, this subject shall not me randomized to any group.

Randomization will be conducted using the REDCap randomization module. REDCap does not use an algorithm to dynamically randomize subjects, but rather a pre-determined, stratified and permutated randomization schedule. The module allows for creating a custom allocation list, which serves as a lookup table for deciding how to randomize subjects. The allocation table is stratified to achieve even study treatment distribution within the following subgroups. Raw coded values corresponding to the table are in parenthesis following their representative category.

- Parkinson's severity (Mild vs Moderate):
 - Mild severity (1) (MDS-UPDRS score < 13 AND Carbidopa/levodopa < 375mg/day) (if taking)
 - Moderate severity (2) (MDS-UPDRS > 13 OR Carbidopa/levodopa ≥ 375 mg/day) (if taking)
- Age: ≤ 50 (1) vs > 50 (2)
- Sex: Male (1) vs Female (2)

Controlling Blinded Information

REDCap system's user privileges can be used to allow only certain users to be able to set up the randomization, perform the randomization, or view the allocation information. All REDCap end users will be blinded and will not have access to the randomization information with exception to the unblinded pharmacist and the personnel who will be responsible in setting up the randomization schedule and performing the randomization.

Blinding for Dose Administration

All subjects, investigators, and site staff will be blinded to treatment assigned.

For the preparation of the investigational product, Unblinded pharmacist (UP) will inject the investigational product into a 250 ml sodium chloride (Saline) infusion bag, cover it with an amber plastic bag and apply the label before delivering it to study site.

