- 4. Principal Investigator may stop the infusion at any time, based upon PI's discretion.
- 5. Malignant Hypertension (180/120 mm/Hg)

Confidential

6. Sudden Severe Hypotension (30-40 mm/Hg drop from pre-infusion level)

If an infusion is stopped for a subject due to an adverse event or serious adverse event, including but not limited to hypersensitivity reaction/anaphylaxis, no additional study treatment will be given to the study participant who develops the event. Although, the study participant will not receive the investigational product, he or she must be followed for safety purposes according to the protocol.

Study Stopping Rules

This Clinical Trial will stop if any of the following events are present:

- 1. Subject's Death.
- 2. Occurrence of any thromboembolic event during or after HB-adMSCs administrations (up to 72 hours).
- 3. Any cerebrovascular ischemia or seizure event occurring within 72 hours after any of the investigational product administrations.
- 4. Any Serious Adverse Events determined to be related to the following:
 - When there is one CTCAE.v5 grade 4 or 5 AE, irrespective of attribution.
 - Either any CTCAE Grade 2 adverse event that persists for more than two weeks, or any Grade 3 adverse event, that occurs within 72 hours after product administration.

Should the study participant discontinue study treatment he/she will be followed for safety according to the protocol safety monitoring plan. The study participant will receive follow up communication to ascertain the outcome until resolved fully. All will be documented as per protocol.

Statistical Methods

Sample size consists of up to 24 subjects who have been diagnosed with Parkinson's disease. All data collected from subjects who are enrolled and received the investigational product will be analyzed. The incidence of Adverse Events and Serious Adverse Events will be recorded and reported. Efficacy will be measured by improvement of subject's signs and symptoms associated with Parkinson's disease. Interim analysis of all safety and efficacy data may be performed at any time deemed appropriate by the Sponsor. Although, the subject's data may be analyzed at any time, a data analysis of all available data will be conducted when a least 10 subjects in each group have completed Week 24. Data may be analyzed for internal informational purposes, reports, presentations, and manuscripts.

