• To investigate the safety and efficacy of intravenous infusions of HB-adMSCs vs Placebo in patients with Parkinson's disease as determined by improvements in Quality of Life, estimated by the MDS UPDRS assessment. (Time frame: Baseline to Weeks 4, 8, 16, 24, 32, 42 and 52). A battery of statistical tests will be applied, where suitable and applicable. Tests will include the report of parametric or non-parametric statistical tests, with the corresponding p-values, presented in pair-wise manner, as well as contingency tables, representing answers in their native form.	 Change from Baseline in Total MDS-UPDRS Part II, only at Week 52 Number of treatment-emergent Adverse Event (TEAEs) during 52 week period Number of serious Adverse Events (SAEs) during the period of 52 weeks Number of AEs of special interest includes thromboembolic events, peripheral events defined as thromboembolism of the extremities, infections and hypersensitivities Change from baseline in clinical parameters, measured at the end of the study (52 weeks): Physical examination Electrocardiogram (ECG) Pulse Systolic blood pressure Body weight BMI Change from baseline in laboratory assessments at the end of the study (52 weeks):

Protocol Number: HBPD03

Date: 18-Apr-2023 Version: 2.0 Hope Biosciences Statistical Analysis Plan Status: Final

Objectives	Endpoints
	o Biochemistry
	 Haematology
	 Urinalysis
Secondary Objectives	Secondary Endpoints
To evaluate the safety and efficacy of intravenous infusions of HB-adMSCs vs Placebo in patients with Parkinson's disease based on	Change from Baseline in MDS- UPDRS Total score, at all the timepoints collected, during the period of study (52 Weeks)
changes in disease assessments and dosage of medications. (Time frame: Baseline to Weeks 4, 8, 16, 24, 32, 42 and 52).	 Change from Baseline in Total MDS- UPDRS Part I, at all the timepoints collected during the period of study (52 Weeks)
	 Change from Baseline in Total MDS- UPDRS Part II, at all the timepoints collected during the period of study (52 Weeks)
	 Change from Baseline in Total MDS- UPDRS Part III at all the timepoints collected during the period of study (52 Weeks)
	 Change from Baseline in Total MDS- UPDRS Part IV, at all the timepoints collected during the period of study (52 Weeks)
	 Change from Baseline in Total Neuro- Quality of Life Assessments scores (Neuro-QOL), at all the timepoints collected during the period of study (52 Weeks)

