2.3. Statistical Hypotheses

The null hypothesis states that there is no significant difference in primary efficacy endpoint, Change from Baseline in the total MDS-UPDRS Part II score, compared to the value at Week 52, between the HB-adMSCs and Placebo treatment groups. The alternative hypothesis is that there is a significant difference between the HB-adMSCs and Placebo treatment groups, meaning that the treatment was effective. The hypothesis will be tested using 5% significance level (two-sided).

All other secondary endpoints are tested as exploratory analysis. The criteria will be the same as for the primary endpoint, 5% significance level, two-sided tests, which is a standard in biology and medicine.

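### The protocol does not secure MDS-UPDRS Part II at Week 52 for participants who stop infusions but stay in the study

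*Protocol*

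**What the plan says.** **Endpoint.** The SAP's objectives and endpoints table gives the primary efficacy endpoint as "Change from Baseline in Total MDS-UPDRS Part II, only at Week 52".

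**After an infusion is stopped.** Under Infusion Stopping Rules, if the stop is due to an adverse event, "no additional study treatment will be given to the study participant who develops the event", and then "he or she must be followed for safety purposes according to the protocol". Under Study Stopping Rules a broader sentence reads "Should the study participant discontinue study treatment he/she will be followed for safety according to the protocol safety monitoring plan".

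**After leaving the trial.** The Investigational Plan says "For study participants who do not complete the study trial, a safety follow-up visit will be scheduled": about 30 days after the dose for those with one dose, and at no stated time for those with more than one. Withdrawal Criteria repeats the 30-day visit and names only the reason for discontinuation as something to record there.

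**Length of follow-up.** Adverse Event Reporting Period defines study treatment follow-up as about 20 weeks from the last administration.

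**General schedule.** The Investigational Plan expects each consenting participant to complete Visits 1 to 9. Table 3 and the visit descriptions place the MDS-UPDRS at Visit 8 (Week 42) and Visit 9 (Week 52). The Visit 8 entry in the Investigational Plan refers to participants who are active, a term it does not define.

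**Analysis.** SAP section 4 limits the efficacy set to randomised participants who received all six infusions, and section 10.1.2.1 rules out imputation. The protocol's Statistical Methods section says that all data from enrolled participants who received product will be analysed.

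**The concern.** Every sentence written specifically for people who stop infusions, or who leave, speaks of safety follow-up. None mentions the MDS-UPDRS. None states that a participant who has stopped infusions but not withdrawn consent still attends at Week 52. A site could follow those sentences to the letter and never obtain the primary outcome for such a participant.

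With 12 per arm, a few missing scores matter. Infusion reactions and vital-sign limits are among the stopping reasons, so stopping could differ between cells and saline. If stoppers in one arm also differ in Part II, the comparison of those who remain is biased. An analysis set can be redefined while the data are still blinded, but a Week 52 score that was never taken cannot be recovered.

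**Working it through.** **1. Does the follow-up written for stoppers reach Week 52?**

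Inputs: infusions at Weeks 0, 4, 8, 16, 24 and 32 (Study Summary); follow-up of 20 weeks after the last administration (Adverse Event Reporting Period); primary time point Week 52. End of follow-up = week of last infusion + 20.

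| Last infusion (week) | Follow-up ends (week) | Short of Week 52 by (weeks) |
|---|---|---|
| 0 | 20 | 32 |
| 4 | 24 | 28 |
| 8 | 28 | 24 |
| 16 | 36 | 16 |
| 24 | 44 | 8 |
| 32 | 52 | 0 |

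Only participants who reach the sixth infusion are carried to Week 52. The safety visit at about 30 days (30/7 = 4.3 weeks) falls at Week 4.3 after a single dose at Week 0. If the same interval were applied after a last infusion at Week 24, it would fall at Week 28.3.

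**2. Does other text close the gap?**

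- The expectation that each participant completes Visits 1 to 9 is general and does not mention stopped infusions.
- The words "he or she must be followed for safety purposes according to the protocol" could point to that full schedule or to the 20-week window. The text does not say which.
- The broader sentence points to a safety monitoring plan, not to Table 3.
- The restriction of Visit 8 to active participants leaves open whether someone off treatment is active.

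**3. How much could it matter?**

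The documents give 24 participants, 12 per arm, tested at 5% two-sided (SAP section 2.3). They give no SD, effect size or stopping rate, so nothing in the plan can be reproduced here and what follows is an illustration.

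One stopper is 1/12 = 8.3% of an arm; two are 16.7%; three are 25.0%.

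Assumptions: no true effect; normal outcomes; stopping only in the active arm; the k participants with the highest stopping propensity are lost; that propensity has correlation ρ with a worse score. Then

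bias = ρ × (sum of the k largest expected normal order statistics for n = 12) / (12 − k).

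The three largest are 1.629, 1.116 and 0.793.

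- k = 1: 1.629/11 = 0.148
- k = 2: (1.629 + 1.116)/10 = 0.274
- k = 3: (1.629 + 1.116 + 0.793)/9 = 0.393

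Bias in SD, favouring active:

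| Lost from active arm | ρ = 0 | ρ = 0.2 | ρ = 0.5 | ρ = 1.0 |
|---|---|---|---|---|
| 1 | 0 | 0.03 | 0.07 | 0.15 |
| 2 | 0 | 0.05 | 0.14 | 0.27 |
| 3 | 0 | 0.08 | 0.20 | 0.39 |

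Simulation with the two-sided Mann-Whitney test agrees to about 0.01 SD. With two lost, false positives favouring active rise from about 2.2% to about 3% at ρ = 0.2, 4% to 4.5% at ρ = 0.5, and 9% at ρ = 1.0.

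**4. What does the SAP do with a score that is collected?**

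A participant stopped before infusion 6 has not received all six infusions, so section 4 removes them from the efficacy set whether or not Week 52 was attended. The bias in step 3 therefore already arises under the SAP as written.

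**The case against.** The strongest reply is that safety follow-up in this protocol already includes the efficacy scale. Visit 8 is itself titled a safety follow-up and lists the MDS-UPDRS, the 20-week safety follow-up period contains Visits 8 and 9, and Visit 9 is described as assessing both safety and efficacy. This stands in part. It rules out the reading that stoppers are followed for safety only: that restriction is not in the text. It does not show that stoppers keep these visits. The 20 weeks are counted from the last administration, so for an early stopper they end before Visit 9.

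A second reply is that the protocol does distinguish people off treatment from people out of the trial: the stopping rules describe the former, while the Investigational Plan and Withdrawal Criteria describe non-completers. The wording does differ, and the non-completer visit should not simply be applied to stoppers. But the distinction is implicit, and no assessment schedule is attached to the first group.

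A third reply is that the illustrated bias belongs to the SAP's analysis set. That is correct, and it shapes the fix. The illustration is also one-sided: all stopping is placed in the active arm, and nothing in the documents ties an acute infusion reaction to Part II months later. At zero correlation there is no bias.

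**Conclusion.** The gap is real and should be closed. Collection of the primary outcome after infusions stop is ambiguous for anyone whose last infusion is before Week 32, and the one follow-up length that is stated ends 8 to 32 weeks before the endpoint.

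Two stronger readings are tempting. A reader might infer that Week 52 scores will be lost; the general schedule allows them to be collected, so they are unsecured, not excluded. A reader might also infer that the missing participants are those in whom treatment failed. The listed reasons are acute reactions, vital-sign limits, refusal and investigator discretion, none of which is lack of efficacy, so any informative loss would mainly concern tolerability.

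The firm figures are the calendar shortfall and 8.3% of an arm per stopper. The range of 0.03 to 0.39 SD rests on assumed stopping and correlation, with the upper end an extreme.

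**What to change.** **Protocol.** In the Investigational Plan, Withdrawal Criteria and both stopping-rule sections, define stopping infusions separately from withdrawing from the study. State that a participant who stops infusions without withdrawing consent attends the remaining Table 3 visits without infusion and completes the Parkinson's assessments, at minimum MDS-UPDRS Part II at Week 52. Define or remove the restriction of Visit 8 to active participants. Nothing here changes a dose or a stopping criterion.

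**SAP.** Reconcile section 4 with the protocol's statement that all data from treated participants will be analysed, so that these participants enter the primary comparison as randomised. Say how a sixth infusion stopped midway is counted. Without this change, the collected scores would not alter the planned primary result.

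**Reporting.** Give, by arm, the number who stopped infusions and the number of these with Part II at Week 52.

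**Cost.** A protocol amendment and a SAP revision, plus a few visits for a few participants. The visits already exist in Table 3.

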A clinical laboratory abnormality should be documented as an adverse event. Any adverse event that results in hospitalization or prolonged hospitalization should be documented and reported as a serious adverse event unless specifically instructed otherwise in this protocol. Any condition responsible for surgery should be documented as an adverse event if the condition meets the criteria for an adverse event. All unresolved adverse events should be followed by the investigator until the events are resolved, the subject is lost to follow-up, or the adverse event is otherwise explained

Serious Adverse Event

Adverse events are classified as serious or non-serious. A *serious adverse event* is any AE that is:

- fatal
- life-threatening
- requires or prolongs hospital stay
- results in persistent or significant disability or incapacity
- a congenital anomaly or birth defect
- an important medical event

Important medical events are those that may not be immediately life threatening but are clearly of major clinical significance. They may jeopardize the subject and may require intervention to prevent one of the other serious outcomes noted above. All adverse events that do not meet any of the criteria for serious should be regarded as *non-serious adverse events*. Serious adverse events that are still ongoing at the end of the study period must be followed up to determine the final outcome. Any serious adverse event that occurs after the study period and is considered possibly related to the study treatment or study participation should be recorded and reported immediately.

Adverse Event Reporting Period

The study period during which adverse events must be reported is normally defined as the period from the initiation of any study procedures to the end of the study treatment follow-up. For this study, the study treatment follow-up is defined as approximately 20 weeks following the last administration of study treatment.

Stopping Rules

Infusion Stopping Rules

Study treatment infusion will be stopped if a least one of the following events occur:

- 1. Allergic reaction as evidenced by severe dyspnea, bronchospasm, or hypoxia after the product has been administered intravenously.
- 2. Patient verbally decline the treatment at any moment prior, or during the infusion.
- 3. Hyperpyrexia develops after infusion administration begins (core body temperature greater than or equal to 104°F).

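### Study stopping rule 4 contradicts itself on attribution and does not match its own bullets on seriousness; rules 2 and 3 leave open which administrations count

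*Protocol*

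**What the plan says.** The Study Stopping Rules (Protocol, Stopping Rules) open with "This Clinical Trial will stop if any of the following events are present" and list four items.

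- **Rule 1:** "Subject's Death", with no attribution condition.
- **Rule 2:** "Occurrence of any thromboembolic event during or after HB-adMSCs administrations (up to 72 hours").
- **Rule 3:** "Any cerebrovascular ischemia or seizure event occurring within 72 hours after any of the investigational product administrations".
- **Rule 4, stem:** "Any Serious Adverse Events determined to be", continued by the underlined word *related* and a pointer to two bullets.
- **Rule 4, first bullet:** "When there is one CTCAE.v5 grade 4 or 5 AE, irrespective of attribution".
- **Rule 4, second bullet:** "Either any CTCAE Grade 2 adverse event that persists for more than two weeks, or any Grade 3 adverse event, that occurs within 72 hours" of product administration.

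The Protocol section Serious Adverse Event defines seriousness by outcome or medical importance, not by CTCAE grade. Any event that meets none of its criteria is classed as non-serious.

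On blinding, the Protocol keeps subjects, investigators and site staff blinded (Blinding for Dose Administration). The unblinded pharmacist holds the assignments. Blinding for Clinical Evaluators allows a physician to be unblinded when an adverse event requires it, as determined by the medical monitor or DSMB.

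No section supplied, in the Protocol or the SAP, says whether the stem or the bullets of rule 4 govern, what the event must be related to, or who decides relatedness for this rule.

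**The concern.** A mandatory stop has to give one answer for one event. In rule 4, two consecutive lines give opposite answers for the same event, depending on whether the reader follows the stem or the first bullet. The seriousness condition raises the same difficulty for both bullets.

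At stake is whether the trial continues. If the bullets govern, one unrelated grade 4 event ends a 24-patient trial, possibly before the Week 52 primary endpoint data exist. If the stem governs, the trial goes on. The question would then have to be settled during the trial, after the event has occurred.

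Rule 2 raises a smaller question. Taken literally, whether a thromboembolic event stops the trial depends on the arm. A decision to stop or continue after such an event would then tend to reveal the allocation.

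**Working it through.** The documents state no stopping probability and no expected event rate, so there is no figure to reproduce. The check is one of wording.

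**Step 1: apply stem and bullets separately to the same event.** Here the stem is read as a filter that requires a serious and related event.

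| Event | Stem as filter | Bullet alone | Conflict? |
|---|---|---|---|
| Death, any attribution | Rule 1 already stops the trial | Rule 1 already stops the trial | No |
| Non-fatal grade 4, serious, judged related | Stop | Stop | No |
| Non-fatal grade 4, serious, judged unrelated, outside rules 2 and 3 | No stop | Stop | Yes, on attribution |
| Grade 3 within 72 hours, not serious, outside rules 2 and 3 | No stop | Stop | Yes, on seriousness |
| Grade 2 lasting over two weeks, arising within 72 hours, not serious, outside rules 2 and 3 | No stop | Stop | Yes, on seriousness |

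The 72-hour limit in the second bullet appears to apply to both grades.

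**Step 2: look for one reading that fits every line.**

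- *The stem filters the bullets.* This is coherent for the second bullet, which is silent on attribution: a grade 2 or 3 event can be serious, because seriousness depends on outcome. It fails for the first bullet, which sets attribution aside.
- *Related loosely means meeting one of the following.* The attribution conflict disappears. The stem still says serious, while the bullets name adverse events by grade, so the seriousness mismatch remains. This reading also leaves the underlining of *related* unexplained.

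Neither reading resolves the whole rule.

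**Step 3: compare rules 2 and 3.** The Protocol uses the term investigational product in two ways. The description of Visit 2 in the Investigational Plan sets it against placebo. Blinding for Dose Administration uses it for whatever the pharmacist injects. If the term includes placebo, rules 2 and 3 cover different administrations. If it excludes placebo, both rules depend on allocation. Either way the text leaves something to be clarified.

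**Step 4: illustration only.** Let *p* be an assumed probability that a patient has a non-fatal grade 4 event outside rules 2 and 3 during the study, independently across 24 patients. Assume also that a quarter of such events are judged related, and take all of them as serious.

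- Stop under the first bullet: 1 − (1 − p)^24
- Stop under the stem: 1 − (1 − p/4)^24
- The readings disagree: the first minus the second

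| Assumed p | First bullet | Stem | Difference |
|---|---|---|---|
| 1% | 21.4% | 5.8% | 15.6% |
| 2% | 38.4% | 11.3% | 27.1% |
| 5% | 70.8% | 26.1% | 44.7% |
| 10% | 92.0% | 45.5% | 46.5% |

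If none of the events were judged related, the stem column would be zero and the difference would equal the first-bullet column. The documents support no particular row.

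**The case against.** The strongest reply is grammatical. The stem names no product or procedure. The object of *related to* is the bullet list itself, so the phrase may be a clumsy way of saying that the event falls under one of the bullets. If so, there is no attribution condition to contradict. This reading is possible. The underlining of *related* counts against it, and the seriousness mismatch survives it.

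A second reply is that the practical gap is narrow. Rules 1 to 3 are equally mandatory and carry no attribution condition, and the sponsor may stop the trial for safety at any time (Withdrawal Criteria; Premature Clinical Trial Termination). This stands. The ambiguity does not prevent a needed halt, and the attribution conflict is mainly confined to unrelated, non-fatal grade 4 events outside rules 2 and 3.

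A reader might also infer more than the text supports:

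- *That rule 4 is the trial's only mandatory halt.* It is one of four.
- *That a lasting grade 2 event at any time ends the trial.* The second bullet appears limited to 72 hours after administration.
- *That rule 2 can be applied only by breaking the blind at the site.* The unblinded pharmacist holds the assignments, and event-triggered unblinding is already provided for. What is unclear is whether the trigger depends on allocation at all.
- *That the DSMB cannot do its job.* The sections supplied give it roles in withdrawal and unblinding, but none names it as the body that applies these stopping rules. They also refer to a safety monitoring plan that is not among the documents.

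**Conclusion.** The point holds as an internal contradiction in a safety decision rule. As written, a non-fatal grade 4 event judged unrelated and outside rules 2 and 3 stops the trial under the first bullet of rule 4 and does not stop it under the stem. Separately, the stem's seriousness condition does not match bullets defined by grade. The difference between rules 2 and 3 is a secondary ambiguity, since the Protocol's use of investigational product is mixed.

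The conclusion on attribution rests on taking *related* in its usual attribution sense. The conclusion on seriousness does not need that assumption. Nothing here alters the primary endpoint or its analysis. The size is unknown: the probabilities above rest on assumed event rates, an assumed share judged related, and independence between patients. They should not be read as estimates of how likely a disputed stop is.

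**What to change.** By protocol amendment, the sponsor should:

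1. Reconcile the stem of rule 4 with its bullets on attribution, and state what the event must be related to if relatedness is a condition.
2. Reconcile the stem with the bullets on seriousness.
3. Reconcile rule 2 with rule 3 on which administrations count. If either trigger depends on allocation, say how it is applied while the trial stays blinded.

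Which reading was intended is for the sponsor and its safety reviewers to decide. The rule need not end up with a single condition for all grades; different conditions for different grades would be coherent if stated plainly.

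The cost is amendment wording, agreement from the safety reviewers, and the FDA and IRB steps that the Protocol already requires for any change (Protocol Amendments). No patients, visits or procedures are added.
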